5.2 Secondary Endpoints

Since this is a phase I study, the primary focus is on safety. However, in a 15 subject dose-escalation study, we will also explore potential efficacy endpoints. Secondary outcomes include: changes in biomarkers of inflammation in blood (calprotectin, MPO, GM-CSF, IL-1 β , IL-6, IL8, IL-17, and TNF- α) between Baseline Day 1 and Day 7 and Day 28, and changes in biomarkers of inflammation in sputum (white cell counts with differentials, IL-1 β , IL-6, IL-8, IL-10, IL-17, GM-CSF, MIP-3 α , TNF- α , and active proteases including neutrophil elastase, α_1 -anti-trypsin, and MMP-9) between Baseline Day 1 and Day 7 and Day 28.

6 SUBJECT SELECTION

6.1 Study Population

Study Population: CF subjects will be recruited from the LeRoy W. Matthews Cystic Fibrosis Center located at Rainbow Babies and Children's Hospital in Cleveland, OH. Our Center provides care for over 200 adult patients with CF. Given the wide interest in hMSCs in CF, we do not anticipate any issues recruiting 15 subjects for this study from our Center. However, should recruitment lag behind projected timelines, we could recruit potential study subjects from nearby CF Centers in Akron, OH, Ann Arbor, MI, Buffalo, NY, Columbus, OH, Pittsburgh, PA, and Toledo, OH. Subjects will be studied for up to 13 months. Screening will be between 10 and 42 days. Study treatment will be Day 1 with a 12-month follow-up. We anticipate 15 months to recruit subjects (due to the 3+3 safety study design, the last subject in a given cohort must complete Visit 5 before the first subject in the next cohort can be enrolled). Subjects who fail screening or who withdraw prior to completing Visit 5 will be replaced. Subjects with a diagnosis of CF who meet the inclusion and exclusion criteria will be eligible for participation in this study. Subjects who fail screening may be re-screened one additional time.

6.2 Inclusion Criteria

1. Male or female 18 years of age and above
2. Confirmed diagnosis of CF as evidenced by 1 or more clinical features consistent with the CF phenotype and 1 or more of the following criteria:
 - a. Sweat chloride equal to or greater than 60 mEq/L by quantitative pilocarpine iontophoresis test (QPIT)
 - b. 2 well-characterized, disease causing mutations in the CFTR gene
3. Clinically stable with no significant changes in health status within 2 weeks prior to screening
4. FEV₁ \geq 40% predicted for age based on the global lung function initiative equations at the screening visit

5. Weight \geq 40 kg at the screening visit
6. Able to perform repeatable, consistent efforts in pulmonary function testing
7. Written informed consent obtained from the subject

6.3 Exclusion Criteria

1. Use of an investigational agent within the 4-week period prior to Visit 1 (Day -42 to -10)
2. Chronic daily (>10 mg) or alternate daily (>20 mg on alternate days) use of systemic corticosteroids within the 4 weeks prior to Visit 1 (Day -42 to -10) or initiation of any dosage of systemic corticosteroids within 72 hours prior to Visit 2 (Day 1)
3. Use of hydroxychloroquine or immunosuppressants
4. Initiation of a new antibiotic (oral, IV, and/or inhaled) that is not part of the subject's maintenance regimen for treatment of acute respiratory symptoms within 2 weeks prior to screening through Visit 2 (Day 1)
5. Initiation of any new chronic therapy (e.g., Pulmozyme[®], hypertonic saline, Kalydeco[®], Orkambi[®], high-dose ibuprofen azithromycin, TOBI[®], Cayston[®], nebulized colistin, bronchodilators, inhaled corticosteroids, etc.) within 4 weeks prior to screening
6. Active treatment for non-tuberculous *Mycobacteria*
7. History of a sputum culture positive for a *Burkholderia cepacia* complex organism in the previous 12 months
8. Current tobacco smoker
9. Oxygen saturation $< 92\%$ on room air at Visit 1 (Day -42 to -10)
10. History of pulmonary hypertension
11. SGOT (ALT) or SGPT (AST) > 2.5 times the upper limit of normal at screening, documented biliary cirrhosis, or portal hypertension
12. Total bilirubin concentration >1.2 mg/dL at screening
13. Creatinine > 1.8 mg/dL at screening
14. Pregnant, breastfeeding, or unwilling to practice birth control between Visit 2 (Day 1) and Telephone Call 3 (Day 56) (acceptable forms of contraception: abstinence, hormonal birth control, intrauterine device, or barrier method plus a spermicidal agent), unless surgically sterilized or postmenopausal
15. Screening hematology with white blood cell count $< 4.5 \times 10^9$ cells/L, hematocrit $< 30\%$, and platelets $< 150 \times 10^9$ platelets/L
16. History of invasive cancer requiring systemic therapy
17. History of organ transplantation
18. Currently listed for lung transplantation or having potential to be listed for lung transplantation in the succeeding 12 calendar months from screening
19. Subject unlikely to complete the study as determined by the Investigator

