4 STUDY DESIGN

4.1 Study Overview

Overview of Study Design. A prospective, single-center, single-dose, dose-escalation, open-label interventional study to evaluate the safety and tolerability of allogeneic hMSCs in 15 clinically stable adult subjects with CF. Because the subject's own cells will contain two CFTR mutations, allogeneic hMSC infusion is being employed in this study. Screening data will be reviewed to determine subject eligibility. Subjects who meet all inclusion criteria and none of the exclusion criteria will be entered into the study. The Tables in Appendix II review the schedule of study visits. After a two to six week screening period, subjects will have the Baseline visit (Days 1-2) where they will undergo a single infusion of up to 5×10^6 allogeneic hMSCs/kg. The CCC and NCRM at Case Western Reserve University have a long-standing approach to identifying, screening and using donors to provide hMSCs. Donors are screened per FDA guidelines for cells and tissues (21 CFR 1271). The FDA guidelines are similar to those used for blood donation by Red Cross. The allogeneic hMSCs used in this study will come from one or two healthy donors who have been well-characterized by the CCC and whose sera test negative for CMV antibodies. Healthy donors will be followed by the PI or designee for any procedure-related AEs. Infusions will be performed in the Dahms Clinical Research Unit at University Hospitals Cleveland Medical Center. Study participants will be monitored for the development of infusion-related toxicities for 24 hours. Subjects will have subsequent study visits on Days 7, 14, 28, Months 3 and 6 and telephone calls on Days 4 (or 5), 21, 56 and Month 12. Subject safety and tolerability of the single dose of hMSCs will be evaluated at the study visits by reviewing subject diaries, interval histories, and subject questionnaires, performing physical examinations and spirometry, and obtaining safety laboratories. In addition to infusion related toxicities, special focus will also be placed upon detecting pulmonary exacerbations since an anti-inflammatory therapy theoretically could suppress the immune system to the point where it leads to increased infectious complications. Appendix I lists the criteria for a pulmonary exacerbation. This study will also explore efficacy endpoints that previously have been shown to be key regulators in CF and/or hMSCs: Serum inflammatory biomarkers (calprotectin, MPO, GM-CSF, IL-1 β , IL-6, IL8, IL-17, and TNF- α), and sputum inflammatory biomarkers (white cell counts with differentials, IL-1 β , IL-6, IL-8, IL-10, IL-17, GM-CSF, MIP-3 α , TNF- α , and active proteases including neutrophil elastase, α_1 -anti-trypsin, and MMP-9). These studies will be repeated on Days 7 and 28 and compared to Baseline values (with-in subject comparison). All subject samples will be archived for future studies to explore the impact on the microbiome and for future translational projects. Finally, an optional diagnostic bone marrow exam will be performed between screening and Day 1 on CF subjects willing to undergo the procedure, banked, and used for future translational studies.

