7.2 Prohibited

- Intravenous antibiotics from 14 days prior to the screening visit through Visit 2 (Day 1)
- Newly prescribed oral or inhaled antibiotics prescribed for acute symptoms from 14 days prior to the screening visit through Visit 2 (Day 1)
- Systemic corticosteroids prescribed for an acute issue or for chronic therapy if the dose exceeds a prednisone equivalent of 10 mg every day or 20 mg on alternate days (maximum allowable dose for chronic systemic corticosteroids is 20 mg of prednisone or its equivalent over a two day period) from screening through Visit 5 (Day 28)
- Hydroxychloroquine from screening through Visit 5 (Day 28)
- Other immunosuppressants from screening through Visit 5 (Day 28)
- The use of an investigational agent within 4 weeks prior to Visit 1 (Day -42 to -10)

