13 PROTOCOL VIOLATIONS

A protocol violation occurs when the subject or investigator, fails to adhere to significant protocol requirements affecting the inclusion, exclusion, subject safety and primary endpoint criteria. Protocol Violations for this study include, but are not limited to, the following:

- Failure to meet inclusion/exclusion criteria
- Use of a prohibited concomitant medication

Failure of the investigators or study staff to comply with Good Clinical Practice (GCP) guidelines will also result in a protocol violation. The medical monitor will determine if a protocol violation will result in withdrawal of a subject. When a protocol violation occurs, it will be discussed with the investigator and a Protocol Violation Form detailing the violation will be generated. This form will be signed by the Investigator. A copy of the form will be filed in the site's regulatory binder.

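### Exclusion 4 and the oral/inhaled rule in 7.2 count the start of an acute antibiotic rather than its receipt, and 6.3 and 7.2 differ in scope for IV antibiotics, so a subject recently off a course can supply the Day 1 baseline

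*Combined protocol and SAP*

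**What the plan says.** **Eligibility.** Section 6.3, item 4 (repeated in the synopsis) excludes "Initiation of a new antibiotic (oral, IV, and/or inhaled) that is not part of the subject's maintenance regimen" when it is given "for treatment of acute respiratory symptoms within 2 weeks prior to screening through Visit 2 (Day 1". The trigger is the start of the course. Section 6.2, item 3 separately asks that the subject be "Clinically stable with no significant changes in health status within 2 weeks prior to screening"; it does not mention antibiotics.

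**Prohibited medication.** Section 7.2 treats the routes differently over the same window:
- IV: "Intravenous antibiotics from 14 days prior to the screening visit through Visit 2 (Day 1". There is no restriction to new courses and no restriction by indication.
- Oral and inhaled: "Newly prescribed oral or inhaled antibiotics prescribed for acute symptoms from 14 days prior to the screening visit through Visit 2 (Day 1". This is tied to a new prescription and to acute symptoms in general, not only respiratory ones.

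**Consequence of a breach.** Section 13 lists "Use of a prohibited concomitant medication" as a protocol violation, and the medical monitor decides whether the subject is withdrawn.

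**Time from screening to infusion.** It is stated in two ways. Section 6.1: "Screening will be between 10 and 42 days". Section 4.1: "After a two to six week screening period, subjects will have the Baseline visit (Days 1-2".

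**Use of the Day 1 sample.** Section 15.2 takes the last pre-infusion measurement as baseline. Change in sputum colony-forming units (CFU) to Days 7 and 28 is on the primary safety list (5.1). Change in sputum inflammatory markers over the same days is a secondary endpoint (5.2), analysed as exploratory (15.4).

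**The concern.** A rule that counts starts does not control exposure. A subject whose acute oral or inhaled course began 15 or more days before screening meets neither the exclusion nor the oral/inhaled prohibition, even if doses continue past the screening visit. That subject's Day 1 sputum may be taken soon after a treatment aimed at the bacteria and inflammation the trial measures, and the Day 7 and Day 28 samples come later still after it. There is no placebo group (8.1), so any return of bacterial load or inflammation after the course cannot be separated from an effect of the cells.

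The plausible direction is apparent worsening. That could hide a benefit or resemble the infectious harm to which 5.1 gives special attention. A relapse needing an antibiotic change, with enough of the Appendix I signs, would also be counted as a post-infusion exacerbation.

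The protocol already accepts this reasoning elsewhere: section 7 requires users of alternate-month inhaled antibiotics to be at the same point of their cycle at Visits 2 to 5.

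For IV courses the issue is one of classification. The Visit 1 and Visit 2 checklists (10.1 and 10.4) call for review of the inclusion and exclusion criteria; they do not name the 7.2 list. A subject can pass that check and still be a violation.

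**Working it through.** The plan gives no figure to reproduce here: 15.6 rests the 15 subjects on feasibility. The check compares the rules and then does date arithmetic.

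**1. The rules side by side**

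| Case | 6.3 item 4 | 7.2 |
|---|---|---|
| Acute oral/inhaled course started before the window, doses continue into it | Passes | Passes on its wording |
| Acute IV course started before the window, doses continue into it | Passes | Breach |
| New IV course in the window, non-respiratory reason | Passes | Breach |
| New oral/inhaled course in the window, acute non-respiratory symptoms | Passes | Breach |

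The first row is the open gap in exposure. The other three are differences in scope.

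**2. Antibiotic-free days at infusion**

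Inputs:
- Latest start that passes item 4: 15 days before screening (two-week window, 6.3).
- Screening-to-infusion interval *I*: 10 to 42 days (6.1), or 14 to 42 days (4.1).
- Time to prepare cells: about 15–20 days of expansion after the investigator's order (8.4), or about 14 days' notice (Appendix II, note l).
- Course length *L*: not in the documents. Assumed 14, 21 and 28 days.

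Put screening at day 0. The course starts on day −15 and its last dose falls on day −15 + *L* − 1. Infusion is on day *I*. Then

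free days = *I* − (−15 + *L* − 1) − 1 = *I* + 15 − *L*.

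| *I* (days) | *L* = 14 | *L* = 21 | *L* = 28 |
|---|---|---|---|
| 10 | 25 − 14 = 11 | 25 − 21 = 4 | 25 − 28 = −3 (still on) |
| 14 | 29 − 14 = 15 | 29 − 21 = 8 | 29 − 28 = 1 |
| 15 | 30 − 14 = 16 | 30 − 21 = 9 | 30 − 28 = 2 |
| 20 | 35 − 14 = 21 | 35 − 21 = 14 | 35 − 28 = 7 |
| 42 | 57 − 14 = 43 | 57 − 21 = 36 | 57 − 28 = 29 |

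Results may shift by a day, depending on how the window boundary and Day 0 are counted. These are the fewest free days for each *I* and *L*; an earlier start leaves more.

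**3. Which rows are realistic**

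Being on the drug up to infusion needs *L* of about *I* + 15: roughly 25 days at *I* = 10, 30 at *I* = 15 and 35 at *I* = 20. An interval of 10 days would require the cells to be ordered before the screening visit, since preparation takes about 14 to 20 days. The rows from 14 to 20 days are therefore the more likely short intervals.

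**4. If receipt were counted instead**

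With no dose from 14 days before screening through Day 1, free days are at least *I* + 14 whatever the course length: 24 at *I* = 10, 29 at *I* = 15, 34 at *I* = 20. The present oral/inhaled wording guarantees no minimum.

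**5. Weight of one subject**

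From Table 1 (8.3.3), one affected subject is 1/3 of cohorts 1 to 3, 1/6 of cohort 4, and 1/15 = 6.7% of the trial.

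**The case against.** The strongest reply is that other provisions already cover most of this.

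- **IV use is barred.** Section 7.1 applies the prohibited list together with the exclusions, and the 30-day medication history (7 and 9.1.1) would reveal an IV course. A reader might infer that 6.3 and 7.2 contradict each other. They do not: both can be applied, and 7.2 is the stricter. What stands is that eligibility and violation status can disagree for the same subject.
- **Stable medication and stable health are required.** Section 7 asks for unchanged medication from screening to Day 28, and inclusion 3 asks for stability before screening. These will catch some subjects. The first is qualified by medical feasibility; the second is a judgement that someone improving on treatment may satisfy. Neither refers to a recent acute course.
- **Long screening removes the problem.** This is correct, as the 42-day row shows. A reader might infer that subjects will commonly be infused while still on an acute course. That needs a course of about 25 days or more at the shortest interval, which the cell preparation time makes unlikely.
- **The affected outcomes carry limited formal weight.** CFU is presented graphically (15.3), markers are exploratory (15.4), and safety is also examined subject by subject. A reader might infer that dose escalation is distorted because one subject is a third of a cohort. The dose-limiting toxicity definition in 5.1 covers infusion-related allergic toxicities of grade 3 or higher within 24 hours, and baseline sputum does not enter it.
- **Rebound is not quantified.** The documents give no rate or size for a return of bacterial load after a course, so bias is plausible but not measured.

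**Conclusion.** The point holds in a limited form. On their wording, 6.3 item 4 and the oral/inhaled bullet of 7.2 both let through an acute course begun more than 14 days before screening, with no minimum antibiotic-free interval. For IV antibiotics the two sections differ in both the event counted and the indication, and need to be reconciled.

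The realistic case is a subject recently off a course. At intervals of 15 to 20 days, the shortest gaps are 16 to 21 days after a 14-day course, 9 to 14 after a 21-day course, and 2 to 7 after a 28-day course. These figures rest on assumed course lengths and on the latest start that passes. How many subjects would be affected, and by how much their CFU or markers would move, cannot be derived from the documents.

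What is at stake is the interpretability of uncontrolled within-subject changes in CFU and sputum markers, and possibly the exacerbation count. The sample size and the dose-limiting toxicity rule are untouched. The correction is worth making because it is inexpensive, not because the trial's main safety decision depends on it.

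**What to change.** Reconcile 6.3 item 4, exclusion 4 in the synopsis, and the first two bullets of 7.2, keeping the existing window of two weeks before screening through Day 1:

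1. Count receipt of any dose in the window, rather than initiation (6.3) or new prescription (7.2, oral/inhaled).
2. Carry the IV rule of 7.2 into 6.3 with the same scope. Changing only the verb in item 4 would not be enough: IV treatment for a non-respiratory reason would still pass 6.3 and breach 7.2.
3. Use one description of the indication for oral and inhaled courses in both sections. At present 6.3 refers to acute respiratory symptoms and 7.2 to acute symptoms. The choice of scope belongs to the investigators; the two sections need to give the same answer.

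Maintenance regimens stay allowed as 7.1 now provides. No new data are needed, because the 30-day medication history already covers the two weeks before screening and changes in medication are recorded at Visit 2.

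The cost is a few words in three places. A few candidates will have to wait after finishing a course, or use the single re-screen that 6.1 already permits.

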DOSE AND MODE OF ADMINISTRATION	dose escalation using the “3+3” design ¹ will be employed. The three doses are 1×10^6 , 3×10^6 , and 5×10^6 hMSCs/kg. Allogeneic MSCs will be derived from bone marrow aspirates from a healthy donor whose serum tests negative for cytomegalovirus (CMV) antibodies. Healthy donors will undergo tests for infectious disease and screening for 41 common CFTR mutations. In addition, the MSCs will be validated for in vitro and in vivo efficacy and potency using the in vivo murine pre-clinical model of CF lung infection and inflammation.
CONTROL PRODUCT, DOSE AND MODE OF ADMINISTRATION	NA
DURATION OF SUBJECT PARTICIPATION AND DURATION OF STUDY	Subjects will be studied for approximately 13 months Screening: between 10 and 42 days Treatment: 1 day Follow-up: 12 months We anticipate 15 months to recruit subjects (due to the 3+3 safety study design). The last subject in each cohort must finish Visit 5 before enrolling the first subject in the next cohort.
CONCOMITANT MEDICATIONS	For those on alternate month TOBI® or Cayston® therapy, on/off cycles must be timed such that a subject is at the same phase of a cycle at Visits 2-5. Allowed: All routine chronic CF medications. 
Prohibited: Anti-inflammatory medications (hydroxychloroquine, corticosteroids >10mg daily or >20 mg on alternate days) and immunosuppressants between Visits 1 and 5. Changes in chronic treatment of CF (e.g., introduction, dose escalation, or elimination of chronic therapies) between Visits 1 and 5.
SAFETY EVALUATIONS	Dose-limiting toxicities, adverse events, including pulmonary exacerbations; Cystic Fibrosis Respiratory Symptom Diary (CFRSD); Respiratory and Systemic Symptoms Questionnaire (RSSQ); physical examination; assessment of vital signs, including oxygen saturation; spirometry, sputum bacterial culture (quantitative and qualitative); hematology, comprehensive chemistry, erythrocyte sedimentation rate (ESR), high-sensitivity C-reactive protein (hs-CRP), and urinalysis

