7 CONCURRENT MEDICATIONS

All subjects should be maintained on the same medications from screening through Visit 5 (Day 28), as medically feasible, with no introduction of new chronic therapies. Medication history will be collected for all drugs for the 30 days prior to screening. If any changes in concomitant medications are required due to AEs (i.e. illness, laboratory abnormalities, surgical procedures, etc.), the reason(s) for the change(s) must be documented. Subjects who require treatment for a pulmonary exacerbation during the course of the trial will remain in the study.

Subjects who have routinely taken more than 10 mg/day (or >20 mg on alternate days) of prednisone or other systemic corticosteroids 4 weeks prior to Visit 1 (Day -42 to -10) or who have taken these medications as needed within 72 hours prior to Visit 1 or 2 will be excluded from participation. Subjects may be re-screened once. For those subjects taking alternate month TOBI® or Cayston® therapy, on/off cycles must be timed such that a subject is at the same phase of a cycle at Visits 2, 3, 4, and 5.

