7.1 Allowed

Except as noted in the prohibited medications section below or in the exclusion criteria described above, all usual CF medications and treatments are allowed. A stable therapeutic regimen (including physiotherapy) between screening and Visit 5 (Day 28) is the goal. Ongoing *chronic* treatment (> 4 weeks prior to screening) with Pulmozyme®, Cayston®, TOBI®, nebulized colistin, Kalydeco®, Orkambi®, high-dose ibuprofen, hypertonic saline, azithromycin, systemic or inhaled corticosteroids, short and long acting bronchodilators and airway clearance is allowed. Unless otherwise medically indicated, subjects not using these therapies should not be started on them from screening through Visit 5 (Day 28) and subjects that have been using them chronically should be encouraged to continue them through Visit 5 (Day 28). Limited use of over-the-counter anti-inflammatory drugs (acetaminophen, aspirin, ibuprofen, or naproxen) from screening through Visit 5 (Day 28) is acceptable.

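### Exclusion 5 bars starting a chronic CF therapy in the 4 weeks before screening but not stopping one or changing its dose, so part of that effect can appear as change after infusion

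*Combined protocol and SAP*

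**What the plan says.** **Before screening.** Exclusion 5 in section 6.3, repeated in the synopsis, begins "Initiation of any new chronic therapy (e.g., Pulmozyme". After a list of further examples (among them high-dose ibuprofen, azithromycin and inhaled antibiotics) it ends "inhaled corticosteroids, etc.) within 4 weeks prior to screening". The only event it names is starting a therapy.

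**From screening onward.** The synopsis, under Concomitant Medications, prohibits a wider set of events: "Changes in chronic treatment of CF (e.g., introduction, dose escalation, or elimination of chronic therapies) between Visits 1 and 5". The body text is softer. Section 7 states "All subjects should be maintained on the same medications from screening through Visit 5 (Day 28), as medically feasible", and section 7.1 adds that "subjects that have been using them chronically should be encouraged to continue them through Visit 5 (Day 28". Section 7.2, the list of prohibited medications, does not repeat the synopsis rule on stopping or dose change.

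**Related criteria.** Inclusion 3 requires "Clinically stable with no significant changes in health status within 2 weeks prior to screening". Exclusions 2 and 3 cover systemic corticosteroids above a threshold, hydroxychloroquine and immunosuppressants.

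**Data available.** Section 7 states "Medication history will be collected for all drugs for the 30 days prior to screening". Section 9.1.1 specifies that dose, frequency and dates are recorded.

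**Use of the outcomes.** Section 8.1 states that there is no placebo group. Section 4.1 compares the Day 7 and Day 28 biomarkers with Baseline within subject. Section 15.2 defines Baseline as the last measurement before infusion.

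**The concern.** The plan treats a recent start of a chronic therapy as a threat to interpretation. It also treats elimination and dose escalation as such a threat from Visit 1 onward. It does not apply the same reasoning to the 4 weeks before Visit 1. A subject who stopped azithromycin or an inhaled antibiotic, or changed its dose, the day before screening meets Exclusion 5. No other criterion clearly catches that subject: inclusion 3 concerns health status rather than regimen, and the stability text in sections 7 and 7.1 starts at screening.

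Without a control group, any drift that continues past Day 1 is inseparable from the infusion. The exposed outcomes are the blood and sputum biomarkers, sputum CFU, spirometry and exacerbation counts. The direction depends on the event. Withdrawal of an anti-inflammatory or antibacterial drug could hide a benefit or look like harm, and a dose increase could look like benefit. With three subjects in each escalation cohort, one affected subject carries a third of a cohort summary.

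**Working it through.** The plan gives no figure for this point, so there is nothing to reproduce. The first step compares the texts, and the second sizes the consequence under stated assumptions.

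**Step 1. Which events are covered, and when**

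| Event | 4 weeks before screening | Visit 1 to Visit 5 |
|---|---|---|
| Start of a chronic therapy | Exclusion 5 | Synopsis; sections 7 and 7.1 |
| Stop | Not named | Synopsis; encouragement in 7.1 |
| Dose change | Not named | Synopsis (escalation); section 7 in general terms |
| Stop of systemic corticosteroid from above the threshold | Exclusion 2 (use within 4 weeks) | Not relevant here |
| Stop followed by a change in health status within 2 weeks | Inclusion 3 | Not relevant here |

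The unfilled cells are the gap.

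**Step 2. How much of the effect can fall after Day 1**

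Inputs from the documents:
- Screening lies 10 to 42 days before infusion (section 6.1).
- Baseline is the last pre-infusion value (section 15.2).
- Nominal follow-up is Day 7 and Day 28, so t = 6 or 27 days from Day 1.
- Cohorts are 3 + 3 + 3 + 6 = 15 (Table 1).

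Assumed, not in the documents: after the stop, the log of the marker approaches its new level exponentially with half-life h between 3 and 28 days.

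With k = ln 2 / h, and w the days from stop to Day 1, the share of the total effect arising between Day 1 and follow-up is

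share = exp(−k·w) × (1 − exp(−k·t)).

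| Interval | w | h = 3 | h = 7 | h = 14 | h = 28 |
|---|---|---|---|---|---|
| Day 1 to 28 | 10 | 10% | 35% | 45% | 38% |
| Day 1 to 28 | 42 | 0% | 1.5% | 9% | 17% |
| Day 1 to 28 | 70 | 0% | 0.1% | 2% | 9% |
| Day 1 to 7 | 10 | 7% | 17% | 16% | 11% |
| Day 1 to 7 | 42 | 0% | 0.7% | 3% | 5% |

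A stop on the day of screening gives w = 10 to 42. A stop 28 days earlier gives w = 38 to 70.

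The 45% is not an accident of the half-lives chosen. For w = 10 and t = 27 the share is largest when exp(−27k) = 10/37 = 0.270. It then equals 0.270^(10/27) × (1 − 0.270) = 0.616 × 0.730 = 0.45.

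**Step 3. Effect on a group summary**

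If one of n subjects has total fold change F, and share s of it (on the log scale) falls after Day 1, the geometric mean change is multiplied by F^(s/n).

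- F = 2, s = 0.45, n = 3: 2^0.15 = 1.11, or +11%.
- F = 2, s = 0.45, n = 15: 2^0.03 = 1.02, or +2%.
- F = 2, s = 0.17, n = 3: 2^0.057 = 1.04, or +4%.
- F = 1.5 and F = 3, s = 0.45, n = 3: 1.5^0.15 = 1.06 and 3^0.15 = 1.18, or +6% and +18%.

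Section 15.4 compares the MTD with lower doses. If the top dose is the MTD, that is 9 against 6 subjects. One affected subject with F = 2 and s = 0.45 then shifts its group by 2^(0.45/9) = 1.04 or 2^(0.45/6) = 1.05.

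The fold changes are assumptions, because the documents give none. The calculation applies to measures differenced from Baseline. It does not size the exacerbation counts, for which the documents give no rate.

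**The case against.** **The Day 1 Baseline absorbs most of the effect.** A reader might infer that the whole withdrawal effect is read as change after infusion, so that a doubling moves a three-subject cohort by 2^(1/3) = 1.26, or +26%. The documents do not support this. At least 10 days separate screening from infusion, and Baseline is reset at Day 1. A +26% shift requires a doubling after Day 1. At a 45% share that means a total effect of 2^(1/0.45) = 4.7-fold. This objection stands, and the sizes above already respect it.

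**The dose decision is safe.** A reader might also infer that escalation is compromised. Section 5.1 defines a DLT by grade 3 or higher infusion-related allergic toxicities within 24 hours, and drift over four weeks does not enter that definition. This stands too. The DMC does see cohort data before the next cohort opens (section 14), but the stated rule rests on DLTs.

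**Other criteria already help.** Inclusion 3 and Exclusions 2 and 3 remove some of these subjects. The 30-day history identifies the rest, and section 15.4 plots each subject's profile. This narrows the gap but does not close it, because no rule or planned analysis acts on the history.

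**The two texts govern different periods.** That is true. This is an asymmetry in the plan, not a contradiction.

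**A careless fix would do harm.** Barring any start or stop of a chronic therapy would, read literally, exclude alternate-month TOBI or Cayston users on nearly any screening date, although the synopsis and section 7 expressly admit them. Re-screening 4 weeks later would not help, because the next switch then falls in the window. This stands, and the fix needs an exemption.

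**Conclusion.** The eligibility gap is real: before screening, nothing bars a recent stop or dose change of most listed chronic therapies, although the synopsis treats elimination and dose escalation as changes from Visit 1. The consequence is limited and conditional. Only the part of the effect still evolving after Day 1 can be mistaken for change after infusion.

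Under the assumed exponential course that part is at most about 45% for a stop 10 days before infusion, and 0 to 17% for a stop 42 days before (half-lives 3 to 28 days, nominal visit days). For an assumed total doubling in one subject, the geometric mean of a cohort of three moves by at most about +11%, and that of all 15 by about +2%. How many subjects are affected cannot be known from the documents, and the number may be zero.

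The exploratory biomarkers and the descriptive CFU, spirometry and exacerbation summaries are exposed. The 24-hour DLT is hardly touched. The point deserves correction because no control group can reveal the bias and the repair is cheap.

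**What to change.** 1. **Eligibility text.** Reconcile Exclusion 5, in section 6.3 and the synopsis, with the synopsis's own notion of a change in chronic treatment. It should cover starting a new chronic therapy, or changing the dose of or discontinuing an existing one, within the same 4 weeks before screening. Keep the word new for starts.
2. **Exemptions.** State that scheduled on/off cycling of inhaled antibiotics, which the synopsis and section 7 already manage by phase, and as-needed bronchodilator use are not changes.
3. **Consistency.** Bring sections 7, 7.1 and 7.2 into line with the synopsis rule for Visits 1 to 5.
4. **Subjects already enrolled.** In the SAP that section 15 says is still to be written, use the 30-day medication history (sections 7 and 9.1.1) to flag any subject with such a stop or dose change. Repeat the biomarker, CFU and spirometry summaries without them.

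**Cost.** A short amendment and one sensitivity listing. No new data are needed, because 30 days of history cover a 28-day look-back. An occasional subject will wait up to 4 weeks and use the one re-screen that section 6.1 permits.
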